#### **9.4.4 Supportive analyses**

Not Applicable

#### **9.5 Safety variables**

Adverse and serious adverse events and pregnancies will be summarized.

#### **9.6 Sample size calculation**

The primary objective of this study was set as investigating the effects of Fingolimod on cognitive performance in highly active relapsing remitting multiple sclerosis (RRMS) patients. Thus the primary end-point was planned as evaluating the effects of Fingolimod on cognitive performance in highly active, RRMS patients comparing cognitive performance at baseline and at Month 24, after treatment for two years as assessed by BICAMS battery test.

The Symbol Digit Modalities Test (SDMT) is one of the best known tests for detecting the cognitive impairment in patients with organic cerebral dysfunctions. The SDMT has a high sensitivity in detecting the presence of brain damage with providing data on cognitive functioning over time in response to treatment. The scoring of SDMT varies between 0-110 and in a study which evaluated age-related cognitive decline, baseline SDMT values for 50-64 years age group was 52.9 and for the 65+age group was 45.9 (34).

There are currently various clinical work is on-going for detection of decremental or incremental changes of cognitive function in RRMS patients and in a recent publication by Benedict et al which evaluated cognitive decline in RRMS patients, the mean SDMT score was found to be 53.1 for stable RRMS patients at baseline. In this study, the authors concluded that the increment of decline on SDMT was 3.5 raw score points, or roughly 6%. It was concluded that in overall, there seems to be an emerging consensus that a score change of 3-4 points on SDMT is clinically meaningful (35).

In this study, it is proposed to observe an increase of 3 points in SDMT testing (which roughly equals to 5% increase in SDMT overall score) is meaningful and in our study, with treatment

we may expect a 5% increase in cognitive functioning during a considerably longer duration of treatment and follow-up.

As per published literature, any cognitive improvement on the basis of SDMT test at a rate of % 5 should be evaluated as a significant improvement for RRMS patient with cognitive dysfunction. Thus, in this study we have postulated to reach a 5 % improvement in SDMT test at 24 months when compared to baseline in the cognitively impaired RRMS patients.

Thus, on the basis of percentage improvement expected and by setting alpha at 0.05 and without considering power (no treatment group comparisons will be made); a minimum of 73 RRMS patients has been calculated to be enrolled. However, due to debilitating nature of RRMS as a disease and considerably longer duration of treatment and/or follow-up, a 10 % LFU should be expected and for providing coverage for such cases, 80 RRMS patients should be enrolled to the study.

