## Glossary of terms

Assessment	A procedure used to generate data required by the study
Enrollment	Point/time of patient entry into the study; the point at which informed consent must be obtained (i.e. prior to starting any of the procedures described in the protocol)
Epoch	The planned stage of the subjects' participation in the study. Each epoch serves a purpose in the study as a whole. Typical epochs are: determination of subject eligibility, wash-out of previous treatments, exposure of subject to treatment or to follow-up on subjects after treatment has ended.
Investigational drug	The drug whose properties are being tested in the study; this definition is consistent with US CFR 21 Section 312.3 and is synonymous with "investigational new drug" or "investigational medicinal product."
Investigational treatment	All investigational drug(s) whose properties are being tested in the study as well as their associated treatment controls. This includes any placebos, any active controls, as well as approved drugs used outside of their indication/approved dosage or tested in a fixed combination. Investigational treatment generally does not include other treatments administered as concomitant background therapy required or allowed by the protocol when used within approved indication/dosage
Subject Number	A number assigned to each patient who enrolls into the study
Part	A subdivision of a single protocol into major design components. These parts often are independent of each other and have different populations or objectives. For example, a single dose design, a multiple dose design that are combined into one protocol, or the same design with different patient populations in each part.
Period	A subdivision of a cross-over study
Premature patient withdrawal	Point/time when the patient exits from the study prior to the planned completion of all investigational/study treatment administration and all assessments (including follow-up)
Stop study participation	Point/time at which the patient came in for a final evaluation visit or when study/investigational treatment was discontinued whichever is later
Study drug/ treatment	Any single drug or combination of drugs administered to the patient as part of the required study procedures; includes investigational drug (s), active drug run-ins or background therapy

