## **6.1 Information to be collected on screening failures**

Patients who sign the informed consent form but fail to meet eligibility criteria during the Screening Phase will be considered screening failure and the reason will be documented on the Screening Record CRF.

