### **6.5.2 Electrocardiogram (ECG)**

A standard 12 lead ECG will be performed at screening, right before the intake of the first dose of the study drug and after 6 hours of the intake of the study drug. Interpretation of the tracing must be made by a qualified physician and documented on the ECG section of the CRF. Each ECG tracing should be labeled with the study and subject number, date, and kept in the source documents at the study site. Clinically significant abnormalities should also be recorded on the Medical History/Adverse event CRF page. Clinically significant findings must be discussed with the Novartis Medical Monitor prior to enrolling the patient in the study.

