## **9 Data analysis**

### **9.1 Analysis sets**

Data analysis will be performed after all of the data is collected from the enrolled patients. All RRMS patients will be accepted as the analysis sets.

The statistical analyses of this study will be performed by a Contract Research Organization

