#### **9.4.3.1 Data analysis**

##### **General Approach**

All Statistical analyses will be performed with MedCalc Statistical Software version 13.1.2 (MedCalc Software bvba, Ostend, Belgium; <http://www.medcalc.org>; 2014) at the 5% significance level using 2-sided tests or 2-sided Confidence Intervals.

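### Section 9.6: 80 patients less the stated 10% loss leaves 72, not the minimum of 73, and the plan is inconsistent about when the 80 are counted

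*Combined protocol and SAP*

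**What the plan says.** All references are to the combined protocol and SAP.

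**Size.** Section 9.6 arrives at a minimum of 73 patients, "by setting alpha at 0.05 and without considering power (no treatment group comparisons will be made"), and adds an allowance for loss: "a 10 % LFU should be expected and for providing coverage for such cases, 80 RRMS patients should be enrolled to the study". We read LFU as loss to follow-up.

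**Where the number recurs.** Sections 3.1 and 4 give 80 as a plain number. The Population entry of the synopsis makes it a floor of at least 80.

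**When a patient counts as enrolled.** The Glossary defines enrolment as "the point at which informed consent must be obtained". It also ties the Subject Number to enrolment, and Section 5.4.1 assigns that number when the consent form is signed. Section 3.1 puts screening after consent, and Section 6.1 adds: "Patients who sign the informed consent form but fail to meet eligibility criteria during the Screening Phase will be considered screening failure". Section 6.5.2 uses the word differently. On ECG findings it says: "Clinically significant findings must be discussed with the Novartis Medical Monitor prior to enrolling the patient in the study". Section 6.5.3 repeats this for OCT. Both tests are done at screening, so enrolment in those two sections comes after consent.

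**The concern.** The 80 is presented as enough to absorb a 10% loss and still leave 73. A reader who takes 10% off 80 gets 72, so the only size requirement in the plan is missed, in expectation, by its own figures.

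The second difficulty is what the 80 counts. Under the Glossary, a patient who consents and then fails screening has enrolled. Under Sections 6.5.2 and 6.5.3 that patient has not. A site or monitor could defensibly stop recruitment at 80 consents or at 80 treated patients, and the plan does not say which. Only this ambiguity could make the shortfall larger than one patient.

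**Working it through.** **Inputs, all from Section 9.6:** required number 73; expected loss 10%; planned number 80.

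**1. Reproducing the 80.** No inflation formula is stated. Multiplying up gives 73 × 1.10 = 80.3, which is 80 to the nearest whole number and 81 rounded up. This may be how 80 arose, but that is inference; 80 may simply be a round figure.

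**2. Number retained.** 80 × (1 − 0.10) = 72, one below 73.

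**3. Number needed.** N = 73/(1 − 0.10) = 81.1, rounded up to 82. Check: 81 × 0.90 = 72.9, still short; 82 × 0.90 = 73.8.

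**4. Largest loss that 80 can absorb.** (80 − 73)/80 = 7/80 = 8.75%.

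**5. How firm the shortfall is.** Assume each patient is lost independently with probability 0.10. The number retained from 80 is then Binomial(80, 0.90), and P(at least 73) = 0.446. From 82 it is 0.697. So 80 may well keep 73, and 82 would not guarantee it.

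**6. What one patient is worth.** The plan names no formula for 73. One that matches is the precision of a single proportion of 5% to within ±5 percentage points, with tests and intervals set "at the 5% significance level using 2-sided tests or 2-sided Confidence Intervals": 1.96² × 0.05 × 0.95/0.05² = 72.99, so 73. On that inferred basis the half-width, 1.96 × √(0.05 × 0.95/n), is 5.00 points at n = 73 and 5.03 at n = 72. No conclusion would change.

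**7. The counting point, side by side.**
- At consent: the Glossary entry for enrolment; the Glossary entry for Subject Number read with Section 5.4.1.
- After the screening tests: Sections 6.5.2 and 6.5.3.
- Not explicit: Sections 3.1, 4 and 9.6 and the synopsis, none of which says whether the 80 are consented or treated.

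**8. What the consent reading would do.** With screen-failure proportion s, the expected number retained is 80 × (1 − s) × 0.90. The documents give no value for s, so no result can be attributed to the plan. Purely as an illustration, assumed values of 5%, 10% and 20% give 68.4, 64.8 and 57.6. At s = 0 the result is the 72 of step 2.

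**The case against.** The strongest reply is that nothing of substance turns on this. The gap is one expected patient, the synopsis allows more than 80, and 73 has about a 45% chance of being kept anyway. All of that stands. A reader might infer that 80 cannot deliver 73; the documents do not support that.

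Section 9.6 also describes the 73 themselves as patients to be enrolled, so reading 73 as the number left at Month 24 is an inference. It is the natural one, because an allowance for loss makes sense only if 73 must remain afterwards.

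A reader might also infer that screening failures definitely come out of the 80. That is one reading only. Section 4 speaks of 80 patients included in the study who meet the McDonald criteria, Section 6.1 records screening failures separately, and the Glossary is partly generic (it defines a term for cross-over studies, which this is not). These points favour counting eligible patients. They do not remove the conflict, because numbering at consent puts the Glossary meaning into practice.

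Two further inferences are tempting:
- *That screening failures contaminate the analysis.* Section 9.1 says "Data analysis will be performed after all of the data is collected from the enrolled patients", but that sentence concerns timing. BICAMS is first given at Visit 1, so a screening failure has no scores to contribute to the primary comparison.
- *That the 10% is too small because it omits other exits.* The scope of LFU is not defined, and Section 6.3 (a month off drug) conflicts with Section 5.4.9 (stopping drug is not in itself withdrawal). Those sections must be reconciled; until then, no shortfall can be computed from them.

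Finally, correcting the inflation does not address the basis of 73. Section 9.6 says "we have postulated to reach a 5 % improvement in SDMT test at 24 months when compared to baseline" but gives no standard deviation and sets power aside. That is a separate and larger question, which neither 80 nor 82 settles.

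**Conclusion.** The point holds in a limited form. At the stated 10% loss, 80 patients leave an expected 72, so Section 9.6 is wrong in saying that 80 covers the loss. The documented size of the error is one patient, or equivalently a tolerable loss of 8.75% in place of 10%. This assumes that 73 is the number wanted after loss and that the 10% applies to the 80.

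Separately, the plan uses enrolment in two senses, and gives 80 as a floor in one place and a fixed number in others. If the 80 were counted at consent, every screening failure would reduce the retained number further, but the documents supply no rate and the amount cannot be computed. The illustrative figures in the working depend wholly on assumed rates and on that disputed reading, so they should not be quoted as the plan's shortfall. This is a correction worth making for accuracy; it does not show that the trial is too small.

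**What to change.** 1. In Section 9.6, replace the statement that 80 covers a 10% loss with the figure it delivers: 72 expected at Month 24 at 10% loss. Alternatively, say that 80 retains 73 provided loss does not exceed 8.75%. No extra patients are required. Only if the sponsor wants 73 expected after a 10% loss does the number become 82, two more.
2. In Section 9.6, state that the 80 are counted at first dose (Visit 1).
3. Use that meaning of enrolled throughout. The Glossary entry for enrolment needs rewording, and the Subject Number entry should refer to consented patients, since Section 5.4.1 numbers patients at consent. Sections 6.5.2, 6.5.3 and 9.1 can then be read in the same sense.
4. Make the synopsis agree with Sections 3.1, 4 and 9.6 on whether 80 is a minimum or a fixed number.

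The cost is a wording amendment under Section 11.1. The stated retained number becomes slightly less favourable; procedures and analyses are unchanged.

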## **9.7 Interim analyses**

Interim analysis might be conducted yearly.

## **10 Ethical considerations**

### **10.1 Regulatory and ethical compliance**

This clinical study was designed and shall be implemented and reported in accordance with the ICH Harmonized Tripartite Guidelines for Good Clinical Practice, with applicable local regulations (including European Directive 2001/20/EC, US Code of Federal Regulations Title 21, and Japanese Ministry of Health, Labor, and Welfare), and with the ethical principles laid down in the Declaration of Helsinki.

### **10.2 Informed consent procedures**

Eligible patients may only be included in the study after providing written (witnessed, where required by law or regulation), IRB/IEC-approved informed consent, or, if incapable of doing so, after such consent has been provided by a legally acceptable representative of the patient. In cases where the patient's representative gives consent, the patient should be informed about the study to the extent possible given his/her understanding. If the patient is capable of doing so, he/she should indicate assent by personally signing and dating the written informed consent document or a separate assent form. Informed consent must be obtained before conducting any study-specific procedures (i.e. all of the procedures described in the protocol). The process of obtaining informed consent should be documented in the patient source documents.

Novartis will provide to investigators in a separate document a proposed informed consent form that complies with the ICH GCP guideline and regulatory requirements and is considered appropriate for this study. Any changes to the proposed consent form suggested by the investigator must be agreed to by Novartis before submission to the IRB/IEC, and a copy of the approved version must be provided to the Novartis monitor after IRB/IEC approval.

### **10.3 Responsibilities of the investigator and IRB/IEC**

The protocol and the proposed informed consent form must be reviewed and approved by a properly constituted Institutional Review Board/Independent Ethics Committee/Research Ethics Board (IRB/IEC) before study start. A signed and dated statement that the protocol and informed consent have been approved by the IRB/IEC must be given to Novartis before study initiation. Prior to study start, the investigator is required to sign a protocol signature page confirming his/her agreement to conduct the study in accordance with these documents and all of the instructions and procedures found in this protocol and to give access to all relevant data and records to Novartis monitors, auditors, Novartis Clinical Quality Assurance representatives, designated agents of Novartis, IRBs/IECs, and regulatory authorities as required. If an inspection of the clinical site is requested by a regulatory authority, the investigator must inform Novartis immediately that this request has been made.

### **10.4 Publication of study protocol and results**

Novartis assures that the key design elements of this protocol will be posted in a publicly accessible database such as clinicaltrials.gov. In addition, upon study completion and finalization of the study report the results of this trial will be either submitted for publication and/or posted in a publicly accessible database of clinical trial results.

## **11 Protocol adherence**

Investigators ascertain they will apply due diligence to avoid protocol deviations. Under no circumstances should the investigator contact Novartis or its agents, if any, monitoring the trial to request approval of a protocol deviation, as requests to approve deviations will not be granted.

This protocol defines the study objectives, the study procedures and the data to be collected on study participants. Under no circumstances should an investigator collect additional data or conduct any additional procedures for any research related purpose involving any investigational drugs.

If the investigator feels a protocol deviation would improve the conduct of the study this must be considered a protocol amendment, and unless such an amendment is agreed upon by Novartis and approved by the IRB/IEC it cannot be implemented. All significant protocol deviations will be recorded and reported in the CSR.

### **11.1 Protocol Amendments**

Any change or addition to the protocol can only be made in a written protocol amendment that must be approved by Novartis, Health Authorities where required, and the IRB/IEC. Only amendments that are required for patient safety may be implemented prior to IRB/IEC approval. Notwithstanding the need for approval of formal protocol amendments, the investigator is expected to take any immediate action required for the safety of any patient included in this study, even if this action represents a deviation from the protocol. In such cases, Novartis should be notified of this action and the IRB/IEC at the study site should be informed within 10 working days or less, if required by local regulations.

## 13 Appendix 1: 2010 Revisions to the McDonald diagnosis criteria for MS Guidelines from International Panel on the diagnosis of MS

**Table 1: 2010 McDonald MRI Criteria for Demonstration of DIS**

DIS Can Be Demonstrated by  $\geq 1$  T2 Lesiona in at Least 2 of 4 Areas of the CNS:

- Periventricular
- Juxtacortical
- Infratentorial
- Spinal cordb

Based on Swanton et al 2006, 2007.

a Gadolinium enhancement of lesions is not required for DIS.

b If a subject has a brainstem or spinal cord syndrome, the symptomatic lesions are excluded from the Criteria and do not contribute to lesion count.

MRI = magnetic resonance imaging; DIS = lesion dissemination in space; CNS = central nervous system.

**Table 2: 2010 McDonald MRI Criteria for Demonstration of DIT**

DIT Can Be Demonstrated by:

1. A new T2 and/or gadolinium-enhancing lesion(s) on follow-up MRI, with reference to a baseline scan, irrespective of the timing of the baseline MRI
2. Simultaneous presence of asymptomatic gadolinium-enhancing and non-enhancing lesions at any time

Based on Montalban et al 2010.

MRI = magnetic resonance imaging; DIT = lesion dissemination in time.

**Table 3: 2010 McDonald MRI Criteria for Diagnosis of MS in Disease with Progression from Onset**

PPMS May be Diagnosed in Subjects With:

1. One year of disease progression (retrospectively or prospectively determined)
2. Plus 2 of the 3 following criteriaa:
  - A. Evidence for DIS in the brain based on  $\geq 1$  T2b lesions in at least 1 area characteristic for MS (periventricular, juxtacortical, or infratentorial)
  - B. Evidence for DIS in the spinal cord based on  $\geq 2$  T2b lesions in the cord
  - C. Positive CSF (isoelectric focusing evidence of oligoclonal bands and/or elevated IgG index)

a If a subject has a brainstem or spinal cord syndrome, all symptomatic lesions are excluded from the Criteria.

b Gadolinium enhancement of lesions is not required.

MS = multiple sclerosis; PPMS = primary progressive MS; DIS = lesion dissemination in space; CSF = cerebrospinal fluid; IgG = immunoglobulin G.

**Table 4: 2010 McDonald Criteria for Diagnosis of MS**

Clinical Presentation	Additional Data Needed for MS Diagnosis
≥2 attacks a ; objective clinical evidence of ≥2 lesions or objective clinical evidence of 1 lesion with reasonable historical evidence of a prior attack b	None c
≥2 attacks a ; objective clinical evidence of 1 lesion	Dissemination in space, demonstrated by: ≥1 T2 lesion in at least 2 of 4 MS-typical regions of the CNS (periventricular, juxtacortical, infratentorial, or spinal cord) d ; or Await a further clinical attack a implicating a different CNS site
1 attack a ; objective clinical evidence of ≥2 lesions	Dissemination in time, demonstrated by: Simultaneous presence of asymptomatic gadolinium-enhancing and non-enhancing lesions at any time; or A new T2 and/or gadolinium-enhancing lesion(s) on follow-up MRI, irrespective of its timing with reference to a baseline scan; or Await a second clinical attack a
1 attack a ; objective clinical evidence of 1lesion (clinically isolated syndrome)	Dissemination in space and time, demonstrated by: For DIS: ≥1 T2 lesion in at least 2 of 4 MS-typical regions of the CNS (periventricular, juxtacortical, infratentorial, or spinal cord) d ; or Await a second clinical attack a implicating a different CNS site; and For DIT: Simultaneous presence of asymptomatic gadolinium-enhancing and non-enhancing lesions at any time; or A new T2 and/or gadolinium-enhancing lesion(s) on follow-up MRI, irrespective of its timing with reference to a baseline scan; or Await a second clinical attack a
Insidious neurological progression suggestive of MS (PPMS)	1 year of disease progression (retrospectively or prospectively determined) plus 2 of 3 of the following criteria d : 1. Evidence for DIS in the brain based on ≥1 T2 lesions in the MS-characteristic (periventricular, juxtacortical, or infratentorial) regions 2. Evidence for DIS in the spinal cord based on ≥2 T2 lesions in the cord 3. Positive CSF (isoelectric focusing evidence of oligoclonal bands and/or elevated IgG index)

If the Criteria are fulfilled and there is no better explanation for the clinical presentation, the diagnosis is "MS"; if suspicious, but the Criteria are not completely met, the diagnosis is "possible MS"; if another diagnosis arises during the evaluation that better explains the clinical presentation, then the diagnosis is "not MS."

a An attack (relapse; exacerbation) is defined as patient-reported or objectively observed events typical of an acute inflammatory demyelinating event in the CNS, current or historical, with duration of at least 24 hours, in the absence of fever or infection. It should be documented by contemporaneous neurological examination, but some historical events with symptoms and evolution characteristic for MS, but for which no objective neurological findings are documented, can provide reasonable evidence of a prior demyelinating event. Reports of paroxysmal symptoms (historical or current) should, however, consist of multiple episodes occurring over not less than 24 hours. Before a definite diagnosis of MS can be made, at least 1 attack must be corroborated by findings on neurological examination, visual evoked potential response in patients reporting prior visual disturbance, or MRI consistent with demyelination in the area of the CNS implicated in the historical report of neurological symptoms.

b Clinical diagnosis based on objective clinical findings for 2 attacks is most secure. Reasonable historical evidence for 1 past attack, in the absence of documented objective neurological findings, can include historical events with symptoms and evolution characteristics for a prior inflammatory demyelinating event; at least 1 attack, however, must be supported by objective findings.

c No additional tests are required. However, it is desirable that any diagnosis of MS be made with access to imaging based on these Criteria. If imaging or other tests (for instance, CSF) are undertaken and are negative, extreme caution needs to be taken before making a diagnosis of MS, and alternative diagnoses must be considered. There must be no better explanation for the clinical presentation, and objective evidence must be present to support a diagnosis of MS.

d Gadolinium-enhancing lesions are not required; symptomatic lesions are excluded from consideration in subjects with brainstem or spinal cord syndromes.

MS=multiple sclerosis; CNS=central nervous system; MRI=magnetic resonance imaging; DIS = dissemination in space; DIT=dissemination in time; PPMS=primary progressive multiple sclerosis; CSF=cerebrospinal fluid; IgG=immunoglobulin G.
